## Study rationale

Currently, no existing treatment for MS is known to impact chronically inflamed (also known as “chronic active,” “slowly expanding,” or “smoldering”) white matter lesions. In these lesions, in which inflammation may persist for decades, there is substantial destruction of the neuropil, and, as such, these lesions have been proposed to be part of the basis for clinical progression (17). Activated macrophages/microglia are the primary inflammatory cell type in chronic active lesions, and, as such, short-term depletion of these cells might prevent ongoing tissue damage and potentially allow endogenous repair mechanisms to commence. As described above, IL-1Ra is a natural inhibitor of IL-1, produced in the brain primarily by microglia; animal studies further provide evidence of clinical improvement with use of an IL-1 $\beta$  antagonist (26, 28).

Thus, we postulate that using recombinant human IL-1Ra, or anakinra, will inhibit proliferation of activated macrophages/microglia at the edge of chronic active lesions. Restriction of the study to participants with clinically progressive MS, or stable MS with at least mild disability, reflects the current CNS IRB Protocol Template (5.4.17)

lack of good treatment options to arrest or reverse disability in MS, with the goal of ultimately forestalling impaired mobility and cognition.

As there are no prior data by which to gauge the efficacy of anakinra on chronic active lesions in MS, we will initiate treatment at the FDA-approved dose of 100 mg/d SC and increase the dosage by 100 mg/d every 4 weeks to achieve a target dose of 300 mg/d. Dosing will increase if well tolerated by the patients or until the resolution of the paramagnetic rim lesions. Safety and tolerability measures, as well as pharmacokinetic and pharmacodynamic markers of IL-1Ra action in blood and CSF, will also be obtained as part of this study.

## Dosing Considerations

FDA-approved dosage of anakinra for the treatment of RA is 100 mg/day subcutaneous injection. Doses up to 200 mg/day have shown to be safe in RA, and there are reports of safe administration of doses up to 300 mg/day in various rheumatological indications (37). In graft versus host disease (GVHD), doses from 400–3200 mg/d, by Q24H (every 24 hrs) continuous infusion for 7 days, have been attempted, and showed no significant side effects at the highest doses (the only toxicity was transient elevation of transaminases in two patients) (38). We therefore will initiate treatment with anakinra at a dose of 100 mg/day SC, with dose escalation every 4 weeks to a maximum dose of 300 mg/day, unless endpoints (Section 8.4, Section 9.1) are met earlier.

A study comparing anakinra at 3 mg/kg and 10 mg/kg doses showed that the CSF penetration of anakinra in nonhuman primates is 0.2–0.3%. CSF anakinra concentration peaked 1–2 hours post dose. The decline in CSF concentration of anakinra was slower than in serum, such that by the last measurable time point the CSF anakinra concentration was 56% of the serum concentration. Comparing the two doses, exposure in both serum and CSF increased by 3.7-fold at the higher dose, and the CSF penetration was similar (39).

That this degree of brain penetration is potentially effective in clinical situations is demonstrated by the example of NOMID, which is characterized by substantial neuroinflammation. Study evaluating CSF cytokines levels in NOMID patients treated with anakinra showed, that cytokines elevated at baseline, including IL-6, decreased in both plasma and CSF, whereas IP-10/CXCL10 decreased only in CSF (baseline blood levels being similar to controls) (40).

## Rationale for outcome measures

**7-tesla MRI.** As described in Section 0, 7T MRI can detect iron deposition within activated macrophages/microglia at the edge of chronic active white matter lesions, which are the ultimate target of the therapy studied in this protocol. The availability of this outcome measure makes it possible to assess the effects of novel therapies on such lesions.

Since multiple sclerosis is an inflammatory disease of the nervous system, and active CNS inflammation can only be detected by leakage of gadolinium contrast by MRI, the majority of the scans performed under this protocol will require gadolinium contrast.

**Safety and tolerability.** Safety and tolerability will be assessed through patient interview and logging of adverse events (AEs), as well as by lab work and imaging. Since anakinra has not previously been used in the treatment of multiple sclerosis and it is not known if this drug could unexpectedly exacerbate disease inflammatory activity, safety monitoring by imaging will require gadolinium contrast for all scans under this protocol except the Month 24 post treatment follow-up scan; at this latter time-point, gadolinium will only be administered if clinically indicated.

**Blood and CSF biomarkers.** We will collect blood and CSF samples for exploratory analysis of other potential biomarkers of anakinra's efficacy. Techniques to be used may include (but are not limited to) flow cytometry immunophenotyping and cytokine/protein assessments. Specific molecules to be assessed may include (but are not limited to); IL-1 $\beta$ , IL-1Ra, IL-2, IL-6, IL-10, IL-12, IL-18, TNF, IFN $\gamma$ , IP-10/CXCL10, neopterin, and neurofilament light chain.

## 2. Study Objectives

### Primary objectives

The primary objective of this protocol is to evaluate the effects of anakinra treatment on the paramagnetic rim of chronically inflamed white matter lesions, as seen on 7-tesla MRI.

### Secondary objectives

The secondary objectives of this protocol are to collect and analyze additional clinical, imaging, and biological data relevant to the safety and tolerability of anakinra, as well as its mechanism of action.

## 3. Subjects

### Description of study populations

This protocol will enroll up to 10 individuals with progressive or stable MS, evidence of chronic active lesions in the white matter (by MRI), and no evidence of new lesion formation in the prior 3 months or clinical relapse in the prior 12 months (by analysis of prior off-protocol MRI scans). We aim to achieve 5 study completers. NIH employees, regardless of their status as subordinates, relatives, or coworkers of investigators, are eligible.

## Inclusion criteria

### ***Inclusion criteria:***

- Age  $\geq 18$
- Ability to give informed consent
- If fertile, agreement to use an effective method of birth control during the study and for up to 3 months after the last dose of the study drug
- Agreement not to participate in any other interventional study while participating in this protocol
- Diagnosis of MS, either stable or clinically progressive
- Prior 7-tesla MRI scan, with high image quality in the judgment of the study neuroradiologist, demonstrating at least one white matter lesion with a paramagnetic rim (41)

## Exclusion criteria

### ***General exclusion criteria:***

- Pregnancy or current breastfeeding
- Use of another investigational agent within 1 month of screening
- Active infection and or neutropenia (ANC  $< 1000$  cells/ $\mu$ L)
- History of lymphoma
- Known hypersensitivity to administration of anakinra
- Previous treatment with anakinra and/or TNF-receptor inhibitor
- History of asthma
- QuantiFERON-TB gold positive
- Prior treatment with anti-CD20 agent (ocrelizumab, rituximab)
- Prior treatment with anti-CD52 agent (alemtuzumab)
- History or current evidence of any condition, therapy, or laboratory abnormality that might confound the results of the trial or interfere with participation for the full duration of the trial; or not in the best interest of the subject to participate, in the opinion of the treating investigator
- Renal dysfunction, as defined by Clinical Center guidelines for administration of gadolinium
- Liver dysfunction, as indicated by baseline aspartate aminotransferase (AST) or alanine aminotransferase (ALT) greater than 1.5 times the upper limit of normal
- Clinical relapse in the 12 months prior to dosing
- New lesion formation (by comparison of screening MRI to a previous MRI of sufficient quality) in the 3 months prior to dosing
- One or more gadolinium-enhancing lesions on the screening scan
- Change in disease-modifying therapy in the 6 months prior to dosing
- Medical contraindication for 7-tesla MRI (including, but not limited to, any non-organic implant or other device such as a cardiac pacemaker or infusion pump or other metallic implants, objects, or body piercings, that are not MRI-compatible or cannot be removed)

[figure not shown]
CNS IRB Protocol Template (5.4.17)

- Psychological contraindication for 7-tesla MRI (e.g., claustrophobia)
- Contraindication to gadolinium administration.
- Active neoplastic disease or any medical condition, other than MS, that requires concurrent immunosuppression or immunomodulation

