## Anakinra

Anakinra is a recombinant, nonglycosylated form of the human interleukin-1 (IL-1) receptor antagonist (IL-1Ra), produced by recombinant DNA technology using an *E. coli* bacterial expression system. Anakinra consists of 153 amino acids and has a molecular weight of 17.3 kDa. Anakinra belongs to the pharmacological class of IL-1 inhibitors: it blocks the biological activity of IL-1 $\beta$  by competitively inhibiting IL-1 $\beta$  binding to the interleukin-1 type I receptor (IL-1RI), expressed in a wide variety of tissues and organs. Anakinra is FDA-approved for use in rheumatoid arthritis (RA) and the cryopyrin-associated periodic syndrome Neonatal-Onset Multisystem Inflammatory Disease (NOMID) (29).

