### Contraindications, Drug Interactions, Warnings, and Precautions

Anakinra is contraindicated in patients with known hypersensitivity to *E. coli*-derived proteins, anakinra, or any components of the product. Hypersensitivity reactions, including anaphylactic reactions and angioedema have been reported with anakinra.

*TNF-blocking agents:* The use of anakinra in combination with TNF blocking agents is not recommended due to heightened risk of serious infections. In a 24-week study of concurrent anakinra and etanercept (a TNF-blocking agent) therapy in adults with rheumatoid arthritis, the rate of serious infections in the combination arm (7%) was higher than with etanercept alone (0%).

*Vaccinations/Immunizations:* In a placebo-controlled clinical trial (n=126), no difference was detected in anti-tetanus antibody response between the anakinra and placebo treatment groups when the tetanus/diphtheria toxoids vaccine was administered concurrently with Kineret. No data are available on the effects of vaccination with other inactivated antigens in patients receiving Kineret. No data are available on either the effects of live vaccination or the secondary transmission of infection by live vaccines in patients receiving anakinra.

*Pregnancy/Breast-feeding mothers:* There are no adequate and well-controlled studies of anakinra in pregnant women. Animal studies reveal no evidence of impaired fertility or harm to the fetus due to anakinra. Anakinra should not be used during pregnancy unless clearly needed. It is not known whether anakinra is secreted in human milk, and, therefore, it should be used with caution in nursing women.

During the study, if the use of any concomitant treatment becomes necessary (e.g., for treatment of an AE), the treatment will be recorded in the electronic medical record, including the reason for treatment, name of the drug, dosage, route, and date of administration.

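### The hypersensitivity exclusion names only anakinra, although Section 7 of the same protocol contraindicates the drug on three allergy grounds

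*Combined protocol and SAP*

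**What the plan says.** Section 3 (General exclusion criteria) lists "Known hypersensitivity to administration of anakinra". The exclusion list in Appendix 1 repeats the line word for word.

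Section 7 (Contraindications, Drug Interactions, Warnings, and Precautions) is wider. It states "Anakinra is contraindicated in patients with known hypersensitivity to" E. coli-"derived proteins, anakinra, or any components of the product", and adds: "Hypersensitivity reactions, including anaphylactic reactions and angioedema have been reported with anakinra".

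Four other parts of the protocol bear on the point:

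- Section 1 (Anakinra) describes the drug as "produced by recombinant DNA technology using an" E. coli expression system.
- Section 3 separately excludes "Previous treatment with anakinra and/or TNF-receptor inhibitor".
- Section 3 has a general clause covering anyone for whom it is "not in the best interest of the subject to participate, in the opinion of the treating investigator".
- Section 3 also excludes anyone with a "Contraindication to gadolinium administration".

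On dosing, Section 4 (Study overview; Specific procedures) has participants inject themselves after training. A telephone call at 24–48 hours after the first dose is the first scheduled safety contact, and Section 8 repeats that timing. The protocol does not say where the first dose is taken.

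**The concern.** An eligibility list should carry over every ground on which the protocol itself says the study drug must not be given. Here it carries over one of three. A candidate with a known allergy to E. coli-derived proteins, or to an ingredient of the product, meets no specific drug-allergy exclusion and nothing on the checklist prompts the question.

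What is at stake is an avoidable hypersensitivity reaction in someone whose allergy was already known. Section 7 acknowledges that such reactions can be severe. A call a day or two after the first self-injected dose cannot prevent or treat an immediate reaction, so screening is the main written safeguard for these people. No statistical quantity in the plan depends on this line.

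**Working it through.** No arithmetic is involved beyond a count. The check compares the eligibility text with the contraindication text and asks whether any other criterion supplies what is missing.

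**Step 1. Compare the grounds.**

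| Ground for known hypersensitivity | Section 7 contraindication | Section 3 exclusion | Appendix 1 checklist |
|---|---|---|---|
| E. coli-derived proteins | Yes | Not named | Not named |
| Anakinra | Yes | Named | Named |
| Any component of the product | Yes | Not named | Not named |

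Section 7 gives 3 grounds. Section 3 and Appendix 1 each give 1, so 3 − 1 = 2 are omitted, and they are the same two in both places.

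**Step 2. Do the omitted grounds apply to this product?** Yes. Section 1 says the drug is made in E. coli, and Section 7 applies the components ground to the product without qualification.

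**Step 3. How much does the remaining ground do?** Little. A person who knows of a reaction to anakinra will nearly always have been given it, and previous treatment with anakinra is an exclusion in its own right. The allergies that an otherwise eligible, anakinra-naive candidate could know about are mainly the two left out. This is reasoning from the criteria; the documents contain no frequency data.

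**Step 4. Does another criterion fill the gap?**

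- *Best-interest clause.* Read with Section 7, it should lead an investigator who knows of such an allergy to exclude the person. It rests on opinion, however, and names no allergy. The baseline interview in Section 4 confirms the listed criteria, and the only drug-allergy criterion on the list is the narrow one.
- *Gadolinium exclusion.* Section 7 (Risks of study procedures) withholds gadolinium from people with past anaphylaxis to other agents, unless they have had gadolinium before and tolerated it. Through that route the exclusion can reach some people with a severe allergy on an omitted ground. It does not reach those with milder hypersensitivity, or those who have tolerated gadolinium.
- *All other criteria.* None mentions E. coli-derived proteins or product components.

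**Step 5. How were the other Section 7 drug risks handled?** Asthma, tuberculosis, neutropenia, lymphoma and TNF blockade each have a specific line in the exclusion list. The hypersensitivity contraindication was carried over only in part.

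**The case against.** The strongest reply is that the protocol already settles the matter. Section 7 is current protocol text, and an investigator who knows of such an allergy has little room to judge participation to be in the person's interest when the protocol calls the only study drug contraindicated. On this view the list lacks a prompt; it does not give permission to enrol. That is largely right, and it is a main reason the severity is low. It still leaves a stated contraindication to individual judgement and recall when a fixed criterion could cover it.

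A second reply is that the line speaks of the administration of anakinra, which could take in the whole administered product, and that a narrow reading leaves it almost nothing to do. This has some force for the components ground. Section 7, however, lists anakinra and the components separately, so the protocol itself distinguishes them, and E. coli-derived proteins cannot readily be read into the line. Even on the generous reading one ground stays uncovered.

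A third reply is that screening takes place under separate Neuroimmunology Clinic protocols, which may include a full allergy history. Those protocols are not available here, so it cannot be said that the allergies would be missed in practice. Equally, nothing in this protocol requires that they be asked about. This point stands as a limit on what can be claimed.

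It is also fair to say that the timing of the first safety call is a matter of first-dose supervision and would be unchanged by rewording the criterion. It is relevant only to how serious a missed allergy could be.

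**Conclusion.** The concern holds. The exclusion line and its copy in the checklist each name 1 of the 3 hypersensitivity grounds that the protocol gives as contraindications, and no other criterion names the remaining 2. Existing provisions soften the gap without closing it.

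The mismatch can be read directly from the text and is held with high confidence. Whether it would ever lead to a contraindicated person being dosed is much less certain. Enrolment is capped at 10, with 5 completers as the aim (Section 3), and the documents give no rate for either allergy, so no probability is offered. The conclusion assumes only that eligibility is judged against the criteria as written, without relying on an allergy history that might be taken under another protocol.

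The event is unlikely but potentially serious. The line should be corrected. There is no effect on the primary endpoint, the sample size or the analysis.

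**What to change.** Reword the hypersensitivity item in Section 3, and identically in Appendix 1, so that it excludes anyone with a known hypersensitivity to any of three things: proteins derived from E. coli, anakinra itself, or any component of the product. This matches Section 7 and removes the doubt about how broadly the present wording should be read.

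The cost is one reworded line in the criteria and the same line in the checklist. No procedure, visit or analysis is added.

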## 4. Study Design and Methods

### Study overview

Screening will be done under an existing Neuroimmunology Clinic protocol that allows collection of data required for determining eligibility. Prospective participants who meet eligibility requirements will then provide informed consent and undergo baseline procedures. Following training on self-administration of subcutaneous injections, subjects will be started on initial dose of study drug of 100 mg/d. Participants will have a scheduled follow-up phone call at 24–48 hours following the first dose to assess for any adverse reactions or concerns. Subsequent routine assessment of tolerability and safety will be made at the time of scheduled study visits. For the duration of the study, including dose escalation and follow-up phases, participants will undergo assessments at NIH. Telehealth may be used for conducting routine visits to the NIH Clinical Center. Participants will return at weeks 4 and 8, at which time they will undergo clinic visit, lab work, and 7T brain MRI. As long as no treatment-limiting toxicity is encountered (see “safety endpoints,” Section 8.4) AND the study endpoint is not met (see “efficacy study endpoint,” primary outcome, section 9), the dose will be escalated every 4 weeks to a target dose of 300 mg/day, which will be administered for a further 4 weeks. The final on-treatment study visit will be at week 12. At that time, the drug will be discontinued, with off-treatment visits at weeks 16 and 24 (4 and 12 weeks following treatment discontinuation). The study timeline is in **Error! Reference source not found..**

## Fig. 2

- **MRI at week 24 will be done without Gadolinium, unless clinically indicated.**

Should early drug discontinuation occur, either due to dose-limiting toxicity or to achievement of efficacy endpoint, off-treatment follow-up visits will proceed 4 and 12 weeks after treatment interruption. If a 7T scan cannot be obtained within window at any particular study visit, a 3T MRI can substitute. Leftover biological samples will be stored for future analysis.

All study-related visits are expected to take place in outpatient facilities of the NIH Clinical Center and may last up to one full day, depending on the number of procedures to be performed. If more convenient for the participant or necessary for scheduling, visits may be split over several days (within the prescribed visit window). Participants may be hospitalized and treated for conditions that develop while on-protocol if medically necessary or for convenience. Data will be monitored in real time and fully analyzed once all 5 participants have completed all study procedures.

In the event that circumstances beyond our control preclude the travel of one or more of the study participants to the NIH Clinical Center for a visit, or otherwise would put their health at greater risk (i.e. epidemic or pandemic), we will endeavor to establish capabilities for remote visits for new subjects and existing subjects. Specifically, for safety visits, the study team will arrange for local laboratory studies to be done, and conduct a telehealth visit with the participant. Unscheduled visits, due to safety, may also be conducted remotely through telehealth and/or offsite laboratory and radiologic studies and/or in conjunction with a local physician with the guidance of the study PI. The laboratory studies may be performed through LabCorp, Quest, or with the local physician, and results will be sent to the study team for safety monitoring and oversight. Radiology studies will be arranged through a local, non-study physician, or directly by the study team, at a site close to the participants home area if travel to the NIH is not possible. In the event that subjects are unable to come to the Clinical Center because of safety issues or travel restrictions, required in person procedures, physical exams, neurologic exams, research blood draws, lumbar punctures and MRIs, will be conducted as part of a make-up study visit at the next planned study visit time point or as soon as is safe and feasible.

Since this is an open-label study, results of research procedures may be discussed with the participants.

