- **Weeks 4, 8, and 12.** At each visit, sharps boxes and empty vials will be collected. Participants will undergo a brief clinical interview/exam, lab work (to include clinical laboratory studies required for safety monitoring such as CBC with differential and blood collection for research purposes as detailed in Section 9, Exploratory Outcome Measures), clinical scales and LP (week 12 only), and 7T MRI (with gadolinium, if not contraindicated). We may collect up to 175 mL of blood at the week 4, week 8, and week 12 visit not to exceed the Clinical Center's policy for limits of blood drawn for research purposes. The window for these visits will be  $\pm 7$  days.
- **Week 16 (or 4 weeks after dosing discontinuation).** Participants will undergo a brief clinical interview, lab work (clinical and research), 7T MRI (with gadolinium, if not contraindicated). We may collect up to 155 ml of blood at the week 16 visit. The window for this visit will be  $\pm 7$  days.
- **Week 24 (or 12 weeks after dosing discontinuation).** Participants will undergo a brief clinical interview, lab work (clinical and research), clinical scales, LP, and 7T MRI (without gadolinium, unless clinically indicated). We may collect up to 175 mL of blood at the week 24 visit. The window for this visit will be  $\pm 7$  days.

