## 9. Outcome Measures

### Primary outcome measures

The primary outcome measure is the presence or absence of a paramagnetic rim around chronic active white matter MS lesions, assessed at the end of the dosing period.

Definition of efficacy endpoint: disappearance of one or all paramagnetic phase rims. At each study visit, paramagnetic phase rims will be assessed. For the purposes of dose escalation, if at any on-treatment scan, all paramagnetic rims that were present at baseline are no longer seen, dose escalation will end and the subject will proceed into the post-treatment follow-up phase of the study.

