## 10. Statistical Analysis

### Analysis of data/study outcomes

The primary outcome is the per-patient proportion of lesions in which the paramagnetic rim has been modulated at the end of the dosing period. Proportion of diminished/resolved paramagnetic rims will be analyzed by investigators blinded to time point, reported descriptively, and compared to the assumption of no change off therapy (11, 16) — a reasonable assumption since we have never observed complete disappearance of a chronic rim — via Binomial exact tests.

For the secondary outcome measures, safety and tolerability will be assessed qualitatively; AEs will be tabulated and compared to prior published and unpublished (to the extent possible) data on anakinra. Quantification will include the proportion of participants who start anakinra therapy and complete the full dosing. MRI outcomes will be reduced to scalar measures at various time points. Longitudinal changes in rim presence/absence, T1 relaxation time, and lesion volume will be analyzed by analysis of variance or mixed-effects models (which naturally handle missing data), the latter two in comparison to

CNS IRB Protocol Template (5.4.17)

non-rim lesions. Analyses will be performed both in completers and on an intent-to-treat basis. There will be no interim analysis.

Analysis methods for exploratory outcome measures will be determined by the study team and collaborators at a later time point.

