### Power analysis

Given the previous natural history data, which indicates that only 1 out of 29 individuals experienced subtle changes in the paramagnetic rim over the long term (a period of several years), we would expect that very few to no untreated participants will experience changes in the short time period observed in this study. Thus, even 1 participant experiencing short term changes would potentially be clinically meaningful. Using an estimated null proportion of individuals with lesion changes of 0.01, a cohort of 5 participants achieves 80% power to detect a difference of 0.27 using a one-sided binomial exact test with a significance level of 0.05. The null hypothesis will be rejected if 1 individual experiences at least one lesion change.

Participants who drop out or in whom anakinra is stopped will be replaced, up to the accrual ceiling or until there are 5 completers — whichever comes first.

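### A 3T scan may replace 7T at any visit, and nothing keeps a 7T-to-3T rim comparison out of a primary test that one changed lesion decides

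*Combined protocol and SAP*

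**What the plan says.** The substitution rule is one sentence in Section 4, Study overview: "If a 7T scan cannot be obtained within window at any particular study visit, a 3T MRI can substitute". This is the only mention of 3T in the documents.

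Elsewhere the rim is a 7T measurement:

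- The primary objective (Section 2) is to "evaluate the effects of anakinra treatment on the paramagnetic rim of chronically inflamed white matter lesions, as seen on 7-tesla MRI".
- Eligibility (Section 3) requires a prior 7T scan of high quality showing at least one rim lesion.
- The baseline, week 4, 8, 12, 16 and 24 scans (Section 4, Specific procedures) are scheduled at 7T, with a window of ±7 days for the visits from week 4 on.

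The outcome and analysis text does not mention field strength. Section 9 defines the primary outcome as rim presence or absence around "chronic active white matter MS lesions, assessed at the end of the dosing period". Section 10 defines it as the per-patient proportion of "lesions in which the paramagnetic rim has been modulated at the end of the dosing period", read blind to time point. The Power analysis adds: "The null hypothesis will be rejected if 1 individual experiences at least one lesion change".

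On analysis sets and replacement, Section 10 says "Analyses will be performed both in completers and on an intent-to-treat basis" and "Participants who drop out or in whom anakinra is stopped will be replaced, up to the accrual ceiling or until there are 5 completers".

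**The concern.** As written, a participant's rims can be established at 7T and then judged at 3T at the end of dosing. Any difference between the two reads would mix a drug effect with a scanner effect. The documents describe no 3T rim sequence, give no 3T/7T agreement figure, and do not say whether a 3T read counts, is missing, or goes to a sensitivity analysis.

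The null hypothesis does not cover such a comparison. Section 10 assumes that rims do not change without treatment and cites references 11 and 16. By their titles in the reference list, these are a 7-tesla phase-rim study and a serial 7T phase-imaging study. They are cited for stability from 7T to 7T, and nothing is cited for 7T to 3T.

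Because one changed lesion in one participant rejects the null, a single false change caused by the switch of scanner would be enough for a positive primary result. The same read also feeds dose escalation: under Sections 4 and 9, a scan on which no baseline rim is seen ends dosing, and neither section states the field strength of that scan.

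**Working it through.** **Inputs from Section 10, Power analysis.** n = 5; null proportion p0 = 0.01; difference 0.27, so p1 = 0.01 + 0.27 = 0.28; one-sided exact binomial test at 0.05; reject if at least 1 participant has a changed lesion.

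**1. The plan's own figure.**

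- Attained alpha = 1 − 0.99^5 = 0.0490.
- Power = 1 − 0.72^5 = 0.8065, which reproduces the stated 80%.

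**2. Slack in the rule.** The largest null proportion that keeps alpha at or below 0.05 is 1 − 0.95^(1/5) = 0.0102, against the assumed 0.01. With one participant read at 3T, the added false-change chance that takes alpha to 0.05 is 1 − 0.95/0.99^5 = 0.0010, or about 0.1%.

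**3. A false change at 3T.** The chance m is my assumption, not a document figure. One participant with one rim is read at 3T at the end of dosing, and p0 = 0.01 applies otherwise. The false-positive rate is 1 − 0.99^5 × (1 − m).

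| Assumed m | False-positive rate |
|---|---|
| 0 (all 7T) | 4.9% |
| 2% | 6.8% |
| 5% | 9.7% |
| 10% | 14.4% |
| 20% | 23.9% |

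**4. The opposite error.** If the 3T read instead hides a true change with chance f, power is 1 − 0.72^4 × (1 − 0.28 × (1 − f)). For f = 2%, 5%, 10% and 20% this is 80.5%, 80.3%, 79.9% and 79.1%, against 80.7%. An error in this direction costs little.

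**5. Keeping 3T reads out of the test.** A participant without a 7T end-of-dosing scan cannot contribute an event. If that person is not replaced and counts as no change:

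- one such participant: alpha = 1 − 0.99^4 = 3.9%, power = 1 − 0.72^4 = 73.1%;
- two such participants: alpha = 1 − 0.99^3 = 3.0%, power = 1 − 0.72^3 = 62.7%.

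If each is replaced and the test uses five participants with both 7T scans, alpha stays at 4.9% and power at 80.7%.

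**The case against.** The best defence is that the plan can be read coherently. The objective fixes the rim at 7T, and contrast MRI is needed separately at on-treatment visits for safety, so the 3T fallback may exist only to preserve the safety scan. That is a plausible intention, but the text does not say it: the substitution sentence is unrestricted, and the 7T wording of the objective is not carried into Sections 9 or 10. Even on this reading, the plan does not say what happens to a participant without a 7T end-of-dosing scan. The replacement rule covers dropouts and those in whom anakinra is stopped; someone who finishes dosing but misses the scan is neither.

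The exposure is also limited, and this stands. 3T is a fallback for when 7T cannot be obtained within window. Visits may be split over several days, and people with 7T contraindications are excluded. Section 4 provides make-up MRIs when travel or safety problems keep a participant away, and further 7T scans are scheduled at weeks 16 and 24. These make an uncorroborated false change less likely. None sets a scoring rule, and the later scans are off treatment. Deviation reporting does not clearly close the gap either: it applies to missed procedures, and an allowed substitute may not count as missed.

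Finally, the thin margin comes from the one-event rule itself, and the outcome is also to be reported descriptively. Both points are fair. The 3T rule is one contingent route to a false change.

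A reader might infer that rims are harder to see at 3T, so that the error must run towards false disappearance. The documents say that rims are visible at 7T and say nothing about 3T. A reader might also infer that a rim merely fainter at 3T could matter only under the Section 10 outcome wording. The Power analysis counts any lesion change and bases its null on subtle rim changes, so a fainter rim plausibly counts there too.

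**Conclusion.** The point holds as a gap in the plan with a cheap remedy. The substitution rule admits a cross-field comparison into the primary test, the evidence cited for the null does not cover that comparison, and the test has almost no slack to absorb an error.

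Its size cannot be fixed from the documents. The range of 6.8% to 23.9% rests on assumed error rates for one participant with one rim; it should not be read as this trial's false-positive rate. The direction of any 3T error and the frequency of missed 7T scans are both unknown. If every participant has a 7T baseline and a 7T end-of-dosing scan, the point has no effect. That contingency makes it lower priority.

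**What to change.** State in Sections 4, 9 and 10:

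- The primary rim outcome is scored only from a 7T end-of-dosing scan compared with a 7T baseline. A 7T screening scan that meets the existing one-month rule for baseline data may serve as the baseline.
- Substituted 3T scans serve safety reads. Any 3T rim reads are reported separately, outside the binomial test.
- Whether a participant without a 7T end-of-dosing scan is replaced or stays in the denominator as no change. This should be fixed before any rim is read, and it should be consistent with the completer and intent-to-treat analyses.

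Separately, Section 2 and the text on substitution, early discontinuation of escalation and the efficacy endpoint (Sections 4 and 9) must be reconciled on whether a 3T scan can serve for the efficacy endpoint in dose escalation. I propose no clinical rule.

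The text change is a short paragraph. The statistical cost depends on the convention. Without replacement, power at p1 = 0.28 falls from 80.7% to 73.1% with one such participant and to 62.7% with two. With replacement, alpha and power are kept, at the price of one more enrolment per such participant with its full visit schedule (up to six MRIs, three lumbar punctures and 12 weeks of drug), within the ceiling of 10.
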